All necessary data pertaining to the study from SRAlab will be transferred to UT Southwestern Medical Center. Data (except for blood samples) will be maintained for future use, for indefinite amount of time. All data would be de-identified and stored in a protected database. Researchers only with IRB approval and approval from authorized personnel of this study, would have access to the controlled database of data, to be used to answer questions related specifically to their research study.

SAMPLE SIZE JUSTIFICATION

AIMS 1 and 2: We wish to rule out an effect of hormonal state on motor neuronal excitability. To do this, specified the minimum effect size that we considered meaningful along with high statistical power that minimized the chances of a Type-I error. We conducted statistical simulations to evaluate this scenario. Pooling $N = 30$ OCs and $N = 30$ nOCs that provide daily H-reflexes from soleus muscle (Aim 1) and MSR from 3 quadriceps muscles (VM, VL, RF) over one menstrual cycle provided power = .95 to detect effects as small as an average within-individual correlation of $r = -0.075$ ($R^2 = .005$) between a single hormone and reflex responses across a range of situations. Smaller differences are considered as pragmatically meaningless. This degree of power holds even if menstrual cycles vary from 22 to 32 days, and participants miss an average of 25% (see above) of their lab visits (and assumes the data are missing at random).

AIM 3: To test hypothesis 3, that estradiol will produce a targeted facilitatory influence on lower limb muscles, we used a GEE model that views the mean conditioned MEPs at each ISI as correlated outcomes before separate post-hoc tests for each inter-pulse interval (ISI = 7, 10, 15, 20, 25, 30 ms) and each subject between peak estradiol and baseline hormone concentration (Fig. 7). This synthesis establishes a within-

Form A

IRB Velos	STU-2018-0192 26783
--------------	------------------------

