subject control. Based on preliminary data of four subjects, at each of the 6 ISIs >7 ms (see Fig. 6), a sample size of 20 subjects achieved over 90% power to detect a main effect for a GEE model that pools the ISIs as correlated outcomes. Additionally, we have sufficient power (.80) to follow up a main effect, for each of the six ISIs, to detect differences of 40% or larger from the null hypothesis, with an estimated standard deviation of 37% and with a significance level (alpha) of a Bonferroni-corrected $0.05/6 = 0.008$. To allow for attrition we will aim to enroll 30 subjects in each female cohort. To ensure that our within-subject changes can be attributable to changes in the hormonal milieu, we will enroll $N = 15$ males and test them at multiple occasions.

4.b. List of the study intervention(s) being tested or evaluated under this protocol

 N/A - this study does not test or evaluate an intervention. Skip to item 4.d.			
#	Study intervention(s) being tested or evaluated under the protocol Add or delete rows as needed	Affiliate Place a check next to institution(s) where the intervention will be performed	Local Standard Practice? Indicate whether the intervention is considered acceptable practice locally for applicable institutions
1	Insert study intervention 1 here	 UTSW  PHHS  CMC  THR  TSRH  Other: _____	 Yes  Yes  Yes  Yes  Yes  Yes
2	Insert study intervention 2 here	 UTSW  PHHS  CMC  THR  TSRH  Other: _____	 Yes  Yes  Yes  Yes  Yes  Yes

4.c. Risk:Benefit Analysis of study interventions being tested or evaluated under this protocol

For each study intervention identified in section 6b above, complete a risk:benefit analysis table.

(Two tables are provided, copy & paste additional tables as needed or delete both tables if this study does not test an intervention)

Form A

IRB Velos	STU-2018-0192 26783

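### Aim 3 follow-up tests use single-step Bonferroni; Holm would hold the same family-wise error and is never less powerful, with a gain that is small on the plan's own inputs and larger only under stated conditions

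*Combined protocol and SAP*

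**What the plan says.** The Aim 3 paragraph of the Sample Size Justification (section 4.a) sets out two stages. A GEE first treats the conditioned MEPs at the different ISIs as correlated outcomes. Peak estradiol is then compared with baseline within subjects, using "separate post-hoc tests for each inter-pulse interval (ISI = 7, 10, 15, 20, 25, 30 ms").

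For this second stage the plan claims a power of 0.80 at every one of the six ISIs. The effect it has in view is described as follows: "to detect differences of 40% or larger from the null hypothesis". The spread assumed is 37%, which the plan calls an estimate. The threshold for each test is set "with a significance level (alpha) of a Bonferroni-corrected": 0.05 is divided by six and printed as 0.008. The exact quotient is 0.00833, so 0.008 is rounding.

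The sample size of 20 is given for the GEE main effect, with power above 90%. Enrolment is set at 30 per female cohort to allow for attrition. No step-down procedure is mentioned. The paragraph gives neither the number of ISIs expected to respond nor the correlation between them.

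**The concern.** Single-step Bonferroni holds every one of the six tests to 0.05/6, however many of the others have already been rejected. Holm relaxes the threshold after each rejection and still keeps the family-wise error at 5%, with no assumption about dependence. Any ISI that Bonferroni declares significant, Holm declares significant too.

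The follow-up tests exist to say at which ISIs estradiol acts, so what is at stake is power to locate the effect. The GEE main-effect test is not touched. The question is how large the gain is on the plan's own figures.

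**Working it through.** **Inputs from the plan:** six tests; difference 40%; SD 37%; alpha 0.05/6; n = 20; stated power 0.80 per ISI.

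**Assumptions:** two-sided paired t tests; n = 20 also applies to the follow-up tests; 37% is the SD of the within-subject difference (the plan does not say); correlation between ISIs varied, because none is given. The GEE gate is not modelled.

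**Step 1: the plan's own figure.** Noncentrality = (40/37) × √20 = 4.83. The two-sided critical value at 0.05/6 with 19 df is 2.94. Power is 0.959, not 0.80. A paired t test reaches 0.80 with n = 14. At n = 20 it gives 0.80 if the SD of the difference is about 46.6%: noncentrality (40/46.6) × √20 = 3.84. That SD would arise if 37% were a per-condition SD and the within-subject correlation were about 0.21, since 37 × √(2 × (1 − 0.21)) ≈ 46.6 using the unrounded correlation 0.206. The stated 0.80 may also be meant as a floor, in which case it is met. Both baselines are carried forward.

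**Step 2: the two procedures.** Bonferroni compares every p-value with 0.05/6 = 0.0083. Holm orders them from smallest to largest and compares the k-th with 0.05/(7 − k): 0.0083, 0.0100, 0.0125, 0.0167, 0.0250, 0.0500, stopping at the first failure. The first step is identical to Bonferroni, so Holm rejects something exactly when Bonferroni does.

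**Step 3: power by simulation.** Six correlated paired t tests, 40% effect at the responding ISIs, 40,000 replicates, inter-ISI correlation 0.3–0.6:

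| Setting | ISIs responding | Bonferroni, per ISI | Holm, per ISI |
|---|---|---|---|
| SD of difference 37%, n = 20 | 6 | 0.96 | about 0.99 |
| | 3 | 0.96 | about 0.97 |
| | 1 | 0.96 | 0.96 |
| SD of difference 46.6%, n = 20 (assumed) | 6 | 0.80 | about 0.90–0.92 |
| | 3 | 0.80 | about 0.83 |
| | 1 | 0.80 | 0.80 |
| SD of difference 37%, n = 30 | 6 | 0.998 | about 1.000 |

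With SD 37%, n = 20 and six responding ISIs, power to detect all six goes from 0.81–0.85 to 0.97. Power to detect at least one true effect is the same under both procedures, to within 0.1 point, in every scenario.

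**Step 4: role of correlation.** With SD 37%, n = 20 and six responding ISIs, Holm's per-ISI power is 0.995 at correlation 0 and 0.985 at 0.8, against a constant 0.96 for Bonferroni. Correlation reduces the gain slightly; the number of ISIs with a true effect drives it.

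**Step 5: error control.** Under the global null the simulated family-wise error is the same for both procedures: 0.049 at correlation 0 and 0.045 at 0.5. With some true effects, Holm stays at about 0.05 or less.

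**The case against.** The strongest reply is that nothing here is wrong. Bonferroni is valid, the main inference comes from the GEE, and at 40%/37% with 20 pairs each follow-up test already has power 0.96. Holm then adds at most about 4 points per ISI, and about 0.2 if all 30 enrolled are analysed. Bonferroni also gives simple simultaneous confidence intervals. All of this stands, and it makes the point an optional improvement.

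Three stronger readings are tempting, and the documents do not support them.

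- **Holm is materially more powerful here without qualification.** A gain of 10 points or more per ISI needs both a baseline near 0.80 and a response at all six ISIs. For example, a 32% change at all six ISIs with SD 37% and n = 20 gives 0.81 against 0.91–0.93. But 32% is not a figure from the plan and lies below the 40% it sets out to detect.
- **All six ISIs will respond, because the GEE pools them.** Treating outcomes as correlated does not say that each has a true effect. The plan does not state how many should respond.
- **The gain is largest because the ISIs move together.** If that means correlated, the direction is the reverse (step 4).

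In the other direction, the effect and SD rest on preliminary data from four subjects, so a true effect below 40% or a larger SD is a realistic possibility. In that range Holm's gain is more useful.

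**Conclusion.** The point holds as a low-cost efficiency suggestion. Holm gives the same 5% family-wise protection under any dependence and is never less powerful.

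If 37% is the SD of the paired difference and n = 20, the per-ISI gain is about 3 points with six responding ISIs, about 1 point with three and none with one. The clear gain under that reading is in detecting all six. If 0.80 is the true baseline, the gain is about 10–12 points with six responding ISIs and about 3 with three. The plan does not settle which baseline applies, because it does not define the SD or state the test and sidedness behind the 0.80.

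A reader should not infer that Aim 3 is underpowered or that its error control is faulty: the six tests are valid as planned, and finding at least one responding ISI is unaffected.

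**What to change.** In the Aim 3 paragraph, replace the Bonferroni-corrected per-test level with: *Holm step-down across the six ISI tests, family-wise alpha 0.05*. Keep the Bonferroni power as a lower bound. Make the change before the Aim 3 data are examined.

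The cost is one sentence. The downside is that simple simultaneous confidence intervals would still use the Bonferroni level, so an ISI could be significant under Holm while its Bonferroni interval includes no change; the plan should say which intervals will be reported.

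Two clarifications belong in the same edit. First, state the test, sidedness, n and meaning of the 37% SD behind the 0.80. Second, reconcile "at each of the 6 ISIs >7 ms (see Fig. 6") with the six-value list, which includes 7 ms and has only five values above it. This fixes the family size. With five tests the Bonferroni level would be 0.05/5 = 0.01, and paired power at n = 20 would be 0.966.
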